5.5. Additional Safety Listings

A listing of all AEs and SAEs for the entire study population will be provided.

5.6. Exploratory Computed Tomography (CT) Parameters

The following parameters will be assessed at 30 days and 12 months (where data is available):

- A. Cardiac remodeling (e.g., RV dimensions and volume)
- B. EVOQUE frame dimensions
- C. EVOQUE leaflet assessment
- D. EVOQUE positioning

5.7. Electronic Diary and Activity Monitoring Sub-study

A sub study of up to 10 sites and up to 45 patients (upon FDA approval) with data through 12 months will be conducted as follows:

- A. **Electronic Diary (eDiary):** To measure quality of life improvement in greater detail, electronic patient reported outcomes will be collected via a handheld device. The following assessments will be used to measure quality of life throughout the sub-study period:
 1. KCCQ
 2. EQ-5D-5L
 3. SF-12
 4. Mood questionnaire
 5. Symptom burden

A daily assessment will be administered from baseline (for a minimum of 14 days before the index procedure) and then from post discharge through the 12-month follow-up visit.

- B. **Activity Monitoring:** To measure the improvement in functional status, an activity monitor (wristwatch) will be worn by patients. The monitor is worn from baseline (for a minimum of 14 days before index procedure), paused at time of admission for index procedure, and resumed post discharge and worn through the 12-month follow-up visit.

6. Study Design

This is a prospective, single-arm, multi-center study to evaluate the safety and performance of the EVOQUE system in the treatment of patients with at least moderate TR and signs of, symptoms from, or prior heart failure hospitalizations for TR.

6.1. Number of Planned Patients

Up to 200 patients (upon FDA approval) are planned to be enrolled in this study.

6.2. Number of Planned Clinical Study Sites

Up to 200 patients (upon FDA approval) will be enrolled in this study at up to 30 investigational sites (upon FDA approval) in the US.

6.3. Expected Duration of Patient Participation

All implanted study patients will be assessed for clinical follow-up at the following intervals: discharge, 30 days, 6 months, 12 months and annually thereafter for 5 years post-procedure.

Study enrollment is expected to last approximately 18-24 months followed by 5 years of follow-up.

7. Patient Population

7.1. Demographic and Clinical Characteristics

This clinical study is for adult patients with at least moderate TR and signs of TR, symptoms from TR, or prior heart failure hospitalizations for TR.

Patients who appear to the Local Heart Team (which may include one Cardiologist, one Cardiac Surgeon, one Heart Failure specialist, and one Echocardiographer) to meet the initial study eligibility requirements will be evaluated for study participation by the Clinical Screening Committee. Candidates for this study must meet all of the following inclusion criteria and none of the exclusion criteria.

This study is expected to enroll patients with similar baseline characteristics to previously studied populations of percutaneous TR interventions. The mean age of the first-in-human compassionate use experience with the Edwards EVOQUE device in the treatment of patients with severe TR was 78 years, and we expect that this trial will enroll patients with similar baseline characteristics. Therefore, we

expect that participants will qualify for Medicare coverage through the age criteria and we anticipate that the results of this study will be generalizable to the Medicare population.

7.2. Inclusion Criteria

Patients enrolled must meet ALL of the following criteria in Table 5:

Table 5: Inclusion Criteria

Inclusion Criteria #	Criteria
1	Age \geq 18 years old
2	Despite medical therapy (OMT) per the Local Heart Team, patient has signs of TR (peripheral edema or ascites), symptoms from TR, or prior heart failure hospitalization from TR Note: Medical therapy is at investigator discretion and includes diuretic medications in stable doses, unless patient has documented history of intolerance. In With the exception of prehabilitation, it is recommended no new diuretics be introduced and current diuretic doses be stable (i.e. no decrease of more than ½ or increase of 2x) unless medically required (e.g., severe hypotension or signs and symptoms of hypervolemia) for 30 days prior to the procedure.
3	Functional and/or degenerative TR graded as at least moderate on a transthoracic echocardiogram (assessed by the echo core lab using a 5-grade classification ¹⁶)
4	The Local Heart Team determines that the patient is appropriate for transcatheter tricuspid valve replacement
5	Patient is willing and able to comply with all specified study evaluations and provides written informed consent.

7.3. Exclusion Criteria

Potential patients will be excluded if ANY of the following criteria apply in Table 6:

Table 6: Exclusion Criteria

Exclusion Criteria #	Criteria
1	Tricuspid valve anatomy precluding proper device deployment and function, evaluated by echo core lab and by CT
2	Echocardiographic parameters (any of the following, assessed by echo core lab): 
 LVEF < 25% Echocardiographic evidence of severe right ventricular dysfunction Pulmonary arterial systolic pressure (PASP) > 70 mmHg by echo Doppler or R heart catheterization OR PASP > 2/3 systemic BP with PVR > 5 Wood units after vasodilator challenge, in the absence of symptomatic hypotension or systolic BP < 90 mmHg
3	Previous tricuspid intervention that could interfere with placement of the EVOQUE System
4	Presence of trans-tricuspid pacemaker or defibrillator lead with any of the following: 
 Implanted in the RV within the last 3 months Patient is pacemaker dependent¹ on trans-tricuspid lead without alternative pacing option Which has delivered appropriate ICD therapy

PROPRIETARY DATA: THIS DOCUMENT CONTAINS CONFIDENTIAL AND PROPRIETARY INFORMATION OF EDWARDS LIFESCIENCES, LLC. IT MUST NOT BE REPRODUCED OR DISCLOSED TO THIRD PARTIES WITHOUT PRIOR WRITTEN PERMISSION OF EDWARDS LIFESCIENCES, LLC.

Edwards Lifesciences, Edwards, the stylized E logo, and EVOQUE are trademarks of Edwards Lifesciences Corporation.

Exclusion Criteria #	Criteria
5	Severe aortic, mitral and/or pulmonic valve stenosis and/or regurgitation Note: patients with concomitant mitral or aortic or pulmonic and tricuspid valve disease will have the option of getting their respective valve treated, and wait 60 days post-transcatheter or 90 days after surgical treatment prior to being reassessed for the study
6	Active endocarditis within 3 months or infection requiring antibiotic therapy (oral or intravenous) within 2 weeks of the scheduled implant
7	Hemodynamically significant pericardial effusion
8	Intra-cardiac mass, thrombus, or vegetation. Chronic scarred LV apical or LAA thrombi can be considered.
9	Clinically significant, untreated coronary artery disease requiring revascularization, evidence of acute coronary syndrome, recent myocardial infarction ² within 30 days prior to the index procedure
10	Any percutaneous coronary, intracardiac (e.g., left atrial appendage occlusion, ASD closure, AF ablation, etc.), carotid, endovascular intervention, carotid surgery, within 30 days or cardiac surgery within 90 days prior to the index procedure
11	Need for emergent or urgent surgery for any reason or any planned cardiac surgery within the next 12 months
12	Hemodynamic instability defined as systolic pressure < 90 mmHg with or without afterload reduction, cardiogenic shock or the need for inotropic support or intra-aortic balloon pump or other hemodynamic support device within 30 days of index procedure
13	Resting systolic blood pressure < 90 or > 160 mmHg after repeated measurements
14	Patient with refractory heart failure requiring advanced intervention (i.e. left ventricular assist device, transplantation) (ACC/AHA/ESC/EACTS Stage D heart failure)
15	History of DVT or PE or DVT/PE in the past 6 months prior to index procedure
16	Presence of an occluded or thrombosed IVC filter that would interfere with the delivery catheter
17	Stroke within 90 days prior to the index procedure
18	Modified Rankin Scale \geq 4 disability
19	Severe renal insufficiency with estimated glomerular filtration rate (eGFR) \leq 25 mL/min/1.73m ² or requiring chronic renal replacement therapy at the time of screening committee approval
20	Patients with hepatic insufficiency or cirrhosis with Child-Pugh score Class C
21	Any physical impairment which limits the patient's capacity to complete functional testing due to other medical conditions independent of their TR (e.g., orthopedic condition)
22	Continuous home oxygen for primary severe COPD
23	Chronic anemia with transfusion dependency or Hgb < 9 g/dL not corrected by transfusion at time of screening committee approval
24	Thrombocytopenia (Platelet count < 75,000/mm ³) or thrombocytosis (Platelet count > 750,000/mm ³) at the time of screening committee approval
25	Known bleeding or clotting disorders or patient refuses blood transfusion
26	Active GI bleeding within 3 months of the scheduled implant
27	Current or history of illicit drug use
28	Pregnant or lactating; or female of childbearing potential with a positive pregnancy test within 14 days prior to intervention

PROPRIETARY DATA: THIS DOCUMENT CONTAINS CONFIDENTIAL AND PROPRIETARY INFORMATION OF EDWARDS LIFESCIENCES, LLC. IT MUST NOT BE REPRODUCED OR DISCLOSED TO THIRD PARTIES WITHOUT PRIOR WRITTEN PERMISSION OF EDWARDS LIFESCIENCES, LLC.

Edwards Lifesciences, Edwards, the stylized E logo, and EVOQUE are trademarks of Edwards Lifesciences Corporation.

Exclusion Criteria #	Criteria
29	Patients in whom transesophageal echocardiography is contraindicated or cannot be completed.
30	In the opinion of the investigator, access to the femoral vein with a guide sheath is deemed not feasible (e.g., occluded IVC filter, active DVT, occluded femoral veins).
31	Untreatable hypersensitivity or contraindication to any of the following: all antiplatelets, all anticoagulants, nitinol alloys (nickel and titanium), bovine tissue, glutaraldehyde, or contrast media. Note: Patient must be able to tolerate at least one antiplatelet medication AND one anticoagulant medication
32	Currently participating in another investigational biologic, drug or device study in which the patient has not reached a primary endpoint.
33	Co-morbid condition(s) that, in the opinion of the Investigator, limit life expectancy to < 12 months.
34	Presence of significant congenital heart disease including but not limited to hemodynamically significant atrial septal defect, RV dysplasia, and arrhythmogenic RV.
35	Presence of significant iatrogenic interatrial shunt ($Q_p/Q_s > 1.5$), or persistent/pancyclic (or respirophasic) right-to-left shunt, or right-to-left shunt with resting desaturation ($SpO_2 < 90\%$).
36	Any condition, in the opinion of the investigator, making it unlikely the patient will be able to complete all protocol procedures and follow-ups
37	Other medical, social, or psychological conditions that preclude appropriate consent and follow-up, including patients under guardianship
38	Any patient considered to be part of a vulnerable population

To further clarify exclusion criterion #4, pacemaker dependency is the risk of serious injury or death from sudden pacemaker failure. For exclusion #20, refer to Appendix E for Child-Pugh scoring details. For exclusion criterion #38, the definition of a “vulnerable population” is in Section 15.1.

8. Procedures and Methods

8.1. Site Personnel Training

[Redacted content]

[REDACTED]

[REDACTED]

[REDACTED]

[REDACTED]

8.2. Device and Procedure Training

[REDACTED]

[REDACTED]

[REDACTED]

[REDACTED]

8.3. Informed Consent Procedure

Patient participation in this study is voluntary.

Informed consent shall be obtained in writing from the patient or their legally authorized representative and the process shall be documented before any procedure specific to the clinical study is applied to the patient. The Investigator is responsible for ensuring that patient informed consent is obtained.

The obtaining and documentation of patient informed consent must be in accordance with 21 CFR Part 50, the principles of the Declaration of Helsinki, relevant part of ICH/GCP, ISO 14155, and the local IRB.

The ICF must be approved by the study site's IRB.

If, during the course of the study baseline/screening assessments, a patient is found not to be eligible for inclusion in the study, the patient or their representative should be notified and the reason for ineligibility documented on the screening log/form, and the patient will be exited from the study.

The general process for obtaining informed consent is as follows:

- Study investigator(s) and/or delegated study personnel will approach patients with TR who meet general requirements to assess their interest in participating in the study
- Ensure that the principal investigator or his/her authorized designee conducts the informed consent process;
- Include all aspects of the clinical study that are relevant to the patient's decision to participate throughout the clinical study;
- Avoid any coercion or undue improper influence on, or inducement of, the patient to participate;
- Not waive or appear to waive the patient's legal rights;
- Use native non-technical language that is understandable to the patient;
- Provide ample time for the patient to read and understand the informed consent form and to consider participation in the clinical study;
- Include personally dated signatures of the patient and the principal investigator, or an authorized designee responsible for conducting the informed consent process;
- Provide the patient with a copy of the informed consent form and any other written information; and,
- Ensure important new information is provided to new and existing patients throughout the clinical study.

For the purpose of the study, and based on the local requirements at the site, the patients can initially agree to the transfer of their images to the Sponsor for their evaluation. Upon full review and confirmation of suitability of the patient for both the EVOQUE Tricuspid valve replacement procedure and the study eligibility, the full ICF can then be signed. This process is providing that no study specific exams are being carried out as part of the screening process

The Sponsor must approve any modifications to the ICF prior to submission to the IRB and/or FDA (as required).

Once the Investigator has determined the patient's eligibility, the patient must sign the institution's IRB-approved ICF prior to any study-specific procedures being performed. Failure to provide informed consent renders the patient ineligible for the study.

The ICF will be written in a language understandable to the patient (or authorized representative) and administered only by the Investigator or IRB-approved personnel who speaks a language understandable to the patient (or authorized representative). The Investigator or delegated person administering the consent must sign and date the ICF to indicate that the purpose, risks and benefits of the study were explained to the patient and that their signature was witnessed.

The signed ICF must be retained by the study site for verification during on-site monitoring visits. The Investigator will retain the original consent form, a copy will be filed in the patient's medical record, and a copy will be provided to the patient.

8.4. Case Review

Patients who are considered for participation will be reviewed by the Cardiac Imaging Core Lab and Clinical Screening Committee (CSC). Before a case is submitted for review, the site Principal Investigator and Heart Team will screen the patient for fundamental enrollment criteria. Once fully screened and deemed an appropriate candidate, the site will submit the case for review and approval consideration by the CSC.

8.5. Patient Enrollment

A Screening/Enrollment Log will be maintained to document the screening and enrollment of all patients assessed for study participation. All patients who consent to the study will be entered into the Electronic Data Capture (EDC) system, including screen failures.

8.5.1. Screened Failures

Screening is conducted as follows: all patients considered to qualify for the study are offered the possibility of participating and are thereafter evaluated according to the selection criteria defined in this protocol.

Patients who consent to participate in the study but do not fulfill enrollment criteria will be classified as “screen failures” and will not count towards the overall enrollment. The screen failure reason(s) will be documented.

8.5.2. Provisionally Enrolled

Patients are considered “provisionally enrolled” when they have signed the ICF agreeing to participate in the study and have been deemed eligible for study.

8.5.3. Enrolled Patients

A patient will be considered “enrolled” at the time of skin incision to introduce the EVOQUE System into the body. Enrolled patients will be assigned a unique identification number by the study Sponsor. The patient ID number together with the patient initials shall be used to identify the patient on all study-related documents.

A study procedure should be scheduled within 90 days of a patient signing an informed consent.

8.6. Study Exit Criteria and Procedures

All patients that sign an informed consent document for this study will have the study exit reason documented in the medical record and on the appropriate eCRF. Patients may exit the study for any of the following reasons:

- **Screen Failure:** Patients who are consented to participate in the study, but do not fulfill enrollment criteria.

- **Study Device Attempted but Not Implanted:** Enrolled patient for whom the implant procedure was prematurely aborted will be followed either for 30 days (for only safety evaluations) OR until resolution, stabilization, or is adequate explanation of any implant-related AEs and then exited from the study. Examples include:
 - Procedure attempted (i.e. skin incision to introduce the EVOQUE System) but patient did not receive a study device
- **Study Device Re-intervention/Explant:** Patient who has a surgical re-intervention for study device explant will be followed for 30 days after the re-intervention for safety evaluations only or until resolution of any AEs related to the re-intervention and then exited from the study. Note: a patient who has a percutaneous re-intervention where the study device remains in place will continue to be followed for the duration of the study.
- **Withdrawal**
 - **Patient Withdrawal:** A patient may voluntarily withdraw from the clinical study at any time, without penalty or loss of benefits to which they are otherwise entitled.
 - **Physician Withdrawal:** An Investigator also has the right to withdraw a patient if s/he feels it is in the best interest of the patient to do so.
- **Patient death**
- **Lost to Follow-up**
 - If a patient cannot be reached for a follow-up visit, the Investigator will document contact efforts and/or efforts to obtain hospital records in the appropriate eCRF. If a patient cannot be reached in any way, or misses a visit, the patient will be considered “unable to contact” for that time interval.
 - After 3 documented unsuccessful attempts to make contact, a certified letter will be sent to the patient’s residence. If there is no response after a certified letter is sent, the patient will be classified as “lost to follow-up”.
- **Completion Per Protocol**

Withdrawn patients will not have any study follow-up visits or procedures after the time of study exit. All data collected up until the time of withdrawal, including imaging studies such as echocardiography scans, will be analyzed.

For patients lost to follow-up or withdrawn early, the Sponsor may request the site to search the Social Security Death Index and/or other death registries and, if applicable, request the site to obtain a death certificate.

Withdrawn or lost to follow-up patients will not be replaced.

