5.1. Safety Endpoint

Safety will be analyzed as a composite endpoint of Major Adverse Events (MAEs) at 30 days post-enrollment which includes:

- Cardiovascular mortality
- Myocardial infarction (MI)
- Stroke
- Renal complications requiring unplanned dialysis or renal replacement therapy
- Severe bleeding (includes fatal, life-threatening, extensive, or major bleeding, as defined by MVARC)³
- Non-elective tricuspid valve re-intervention, percutaneous or surgical
- Major access site and vascular complications
- Major cardiac structural complications
- Device-related pulmonary embolism

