Questionnaires (Patient completed)								
Kansas City Cardiomyopathy Questionnaire (KCCQ)	X				X	X	X	X
Patient Edema Questionnaire ^L	X				X	X	X	X
Patient Preference Survey ^M	X							
SF-36v2	X				X	X	X	X
Bloodwork^N								
βHCG (if applicable) ^O	X							
BNP or NT-proBNP	X		X	X	X	X	X	X
Coagulation Panel (PT or PTT; INR for patients on vitamin-K antagonist)	X		X	X	X	X	X	X
Complete Blood Count (CBC; including platelets)	X		X	X	X	X	X	X
Complete Metabolic Panel (CMP; including Albumin, Bilirubin, ALP, ALT, AST, creatinine, BUN)	X		X	X	X	X	X	X
GGT	X		X	X	X	X	X	X
Uric Acid and eGFR	X		X	X	X	X	X	X
Troponin or CK-MB	X		X	X				
Electronic Diary and Activity Monitoring Sub study - Up to 45 patients (upon FDA approval) at up to 10 sites								
eDiary Assessment (KCCQ, EQ-5D-5L, SF-12, mood questionnaire, and symptom burden) ^P	X (daily)					X (daily)		
Activity Monitoring ^Q	X (daily)					X (daily)		

A. Refer to Table 7 for assessment windows

B. Implant procedure should be scheduled within 90 days of consent. Patients who enter the procedure room but who do not have the study procedure attempted (at least skin incision to introduce the Edwards EVOQUE System) will be classified as “non-implanted” and will be followed 30 days for safety. These patients will be exempt from all other study follow up visit procedures.

C. Should be collected at the 30 day and 12-month follow-up visits according to the current version of the acquisition guide unless medically contraindicated or patient refuses.

D. See Appendix C for Katz Index of Independence in Activities of Daily Living

E. mRS will be conducted at baseline for all patients with a history of stroke. For patients who experience a stroke during the study, mRS will be conducted closest to 90 days post event. It is recognized that an assessment of stroke is incomplete without an appropriate measurement of the disability resulting from the stroke, hence, mRS closest to 90 days post event will be used to assess clinical disability. Every effort should be made to have a neurologist or neurology fellow perform the neurological assessments, or alternatively, a trained research team member certified in stroke assessment. mRS can be obtained by a certified research team member via phone interview with the patient or caregiver member if the patient is unable to visit the research office.

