12.4. Safety Endpoint Analysis

The safety endpoint of major adverse events (MAEs) at 30 days shall be analyzed via the Kaplan-Meier (KM) method for implanted population. In addition, the event rates of individual adverse event of MAEs will also be calculated at 30 days, 6 months, and annually by the Kaplan-Meier method:

- Cardiovascular mortality
- Myocardial infarction (MI)
- Stroke
- Renal complications requiring unplanned dialysis or renal replacement therapy
- Severe bleeding (includes fatal, life-threatening, extensive, or major bleeding, as defined by MVARC)
- Non-elective tricuspid valve re-intervention, percutaneous or surgical
- Major access site and vascular complications
- Major cardiac structural complications
- Device-related pulmonary embolism

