#### **ANALYSIS POPULATIONS** 4.

Analysis will be performed for the Enrolled, As-Treated (AT), and Per-Protocol (PP) populations defined below:

- Enrolled Population: All patients enrolled in the study, defined as patients who sign informed consent and have had the study procedure attempted (attempted defined as skin incision for study device). Enrolled population will be used for the safety analyses.
- As-Treated Population: A subset of the enrolled population who have had the study device implanted at • the exit of procedure room. The AT population will be the analysis population for performance and functional endpoint analysis.
- Per-Protocol Population: A subset of the AT population who had no protocol deviations relating to • inclusion and exclusion criteria for the trial.

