### 8.1 Safety Endpoint

The safety endpoint of MAEs at 30 days shall be analyzed via the Kaplan-Meier method for the Enrolled and AT populations. In addition, the event rates of individual component of MAEs will also be calculated at 30 days, 6 months, and annually until 5 years post-procedure by the Kaplan-Meier method:

- Cardiovascular mortality •
- Myocardial infarction (MI) •
- Stroke •
- Renal complications requiring unplanned dialysis or renal replacement therapy •
- Severe bleeding (includes fatal, life-threatening, extensive, or major bleeding, as defined by MVARC) •
- Non-elective tricuspid valve re-intervention, percutaneous or surgical •
- Major access site and vascular complications •
- Major cardiac structural complications •
- Device-related pulmonary embolism

The number and percentage of patients with at least one MAE at 30 days will be summarized. The number of MAE at 30 days, 6 months, and annually will be reported as well. Additional analyses of safety endpoints using the PP population will be performed if there is/are a clinically meaningful difference(s) from the enrolled and AT populations.

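### Protocol 8.6 lets Enrolled patients with an aborted implant leave before day 30, so the 30-day MAE endpoint may be incompletely observed in them

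*Protocol*

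**What the plan says.** **Who is enrolled.** Protocol 8.5.3 counts a patient as enrolled "at the time of skin incision to introduce the EVOQUE System into the body". A patient whose implant is then aborted is therefore Enrolled.

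**How long such a patient is followed.** Protocol 8.6, under the exit category for an attempted but unsuccessful implant, says the patient "will be followed either for 30 days (for only safety evaluations) OR until resolution, stabilization, or is adequate explanation of any implant-related AEs", after which the patient is exited.

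**The endpoint.** Protocol 5.1: "Safety will be analyzed as a composite endpoint of Major Adverse Events (MAEs) at 30 days post-enrollment which includes" nine components.

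**The population.** SAP section 4: "Enrolled population will be used for the safety analyses"; Protocol 12.2 agrees. SAP 8.1: "The safety endpoint of MAEs at 30 days shall be analyzed via the Kaplan-Meier method for the Enrolled and AT populations". Protocol 12.4 differs: the same endpoint "shall be analyzed via the Kaplan-Meier (KM) method for implanted population".

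**Other follow-up statements.**
- The Protocol synopsis and SAP 2.2 list a 30-day assessment for enrolled patients. Protocol 6.3 gives the visit schedule for implanted patients only.
- Table 14 note B (Protocol 8.21) says that patients who enter the procedure room without an attempted procedure "will be followed 30 days for safety", with no earlier alternative.
- Protocol 11.9 follows explanted patients for 30 days, and longer if a related adverse event is still open.

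**The concern.** The two limbs of the 8.6 rule are joined by either/or, and nothing says that the later one governs. A patient with no implant-related AE, or with one that resolves on day 4, satisfies the second limb well before day 30.

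The exit trigger also does not match the endpoint. Only implant-related AEs keep the patient in the study. Cardiovascular death, MI, stroke, renal replacement therapy and severe bleeding count as MAEs with no relatedness condition. A later event of this kind, judged unrelated, is the one most likely to be missed.

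Nothing else clearly recovers it. AE capture stops when participation ends (Protocol section 11). The death-registry search in 8.6 names patients lost to follow-up or withdrawn early, not this exit category. SAP 6.1 and 6.2 censor event-free exits at last participation, and neither document specifies a sensitivity analysis.

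The As-Treated set excludes these patients by definition, so the Enrolled MAE analysis is where harm after a failed attempt should appear. Censoring caused by procedure failure may be informative there.

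**Working it through.** The plan has no figure to reproduce. SAP 2.3 says the sample size has no statistical justification, and neither document states an MAE rate, a performance goal for MAE or an abort rate. What follows is a sensitivity calculation.

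**From the documents.** N = 200 (the maximum). Event-free exits are censored at last participation. For event rates, SAP 6.1 uses as denominator only patients who had the event or were followed to the upper bound of the visit window, here day 30 + 7 = 37 (Protocol Table 13).

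**Assumed.**
- k = 4, 10 or 20 patients not implanted (2%, 5%, 10%).
- 30-day MAE risk of 15% or 25% in implanted and 30% or 50% in non-implanted patients.
- 50%, 80% or 100% of non-implanted patients' MAEs fall before exit.
- 80% of implanted patients' MAEs fall before that same day.
- All event-free non-implanted patients exit then.

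**Kaplan-Meier.** Censoring gives each exited patient the later risk of those who stay, so

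error = (event-free early exits / N) × (later risk in those who stay − later risk in those who left).

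The error is negative only if those who left have the higher later risk.

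**Example A:** k = 10, risks 15% and 50%, half of the non-implanted patients' MAEs before exit.
- Implanted: 190 × 0.15 = 28.5 MAEs, of which 22.8 early and 5.7 late. Non-implanted: 5 MAEs, of which 2.5 early and 2.5 after exit.
- True rate = (28.5 + 5)/200 = 16.75%.
- Kaplan-Meier = 1 − [1 − (22.8 + 2.5)/200] × [1 − 5.7/(190 − 22.8)] = 1 − 0.8735 × 0.9659 = 15.63%, an error of −1.12 points.
- Check by the formula: (7.5/200) × (5.7/167.2 − 2.5/7.5) = 0.0375 × (0.0341 − 0.3333) = −0.0112.
- SAP 6.1 denominator: (28.5 + 2.5)/(190 + 2.5) = 16.10%, an error of −0.65 points.

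**Example B:** the same, but all MAEs in non-implanted patients fall before exit.
- Kaplan-Meier: (5/200) × (0.0341 − 0) = +0.09 points, giving 16.84%.
- SAP 6.1 denominator: 33.5/195 = 17.18%, an error of +0.43 points, because the five event-free exits leave the denominator.

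**Range over all assumed combinations (percentage points):**

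| Not implanted | Kaplan-Meier error | SAP 6.1 denominator error | Most that could go unseen, k/200 |
|---|---|---|---|
| 4 | −0.45 to +0.09 | −0.27 to +0.36 | 2.0 |
| 10 | −1.12 to +0.22 | −0.65 to +0.92 | 5.0 |
| 20 | −2.24 to +0.44 | −1.20 to +1.92 | 10.0 |

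If no MAE follows exit, the Kaplan-Meier error is only +0.03 to +0.44 points. For scale, the 90% confidence interval half-width at an assumed 20% MAE rate is 1.645 × √(0.2 × 0.8/200) = 4.7 points.

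**The case against.** A reader might infer that the endpoint simply goes unobserved in failed procedures and that the MAE rate is therefore biased downward. The documents do not support either step.

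- The same sentence in 8.6 offers 30 days, and AEs are recorded from enrollment to exit. An MAE before exit already counts in a time-to-first-event composite; only first MAEs after exit can be lost. Access-site and structural complications and periprocedural MI (within 48 hours, Appendix A) would tend to come early.
- The synopsis, SAP 2.2 and the explant rule in 11.9 favor reading 30 days as a minimum. On that view this is loose drafting.
- The sign is not fixed, as the working shows.
- Protocol 12.4 places the analysis in the implanted population, and the As-Treated analysis in SAP 8.1 is untouched either way.
- The study is a descriptive feasibility study with no performance goal for MAE.

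Most of this stands and limits the claim. It does not remove it. The synopsis is contradicted by section 6.3. Section 11.9 covers explants only; it shows how a 30-day floor can be worded, and 8.6 is not worded that way. Note B gives its firm 30 days to patients who are not Enrolled, while Enrolled patients have the weaker rule. A site following 8.6 as written may exit a patient early without deviating from it.

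**Conclusion.** The concern holds in limited form. Protocol 8.6 permits exit before day 30 for Enrolled patients with an aborted implant, so their 30-day MAE outcome may be incompletely observed and their censoring may be informative.

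The size is unknown. Under the assumed rates, with 2% to 10% not implanted, the Kaplan-Meier error lies between about −2.2 and +0.4 points. The negative end requires 10% not implanted, a 50% MAE risk in them, and half of those events after exit. If the SAP 6.1 denominator is applied to the MAE percentage that SAP 8.1 also reports, that figure can err upward, so the two summaries can diverge because of the same patients.

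Neither a fixed downward bias nor a complete loss of the endpoint in these patients follows from the documents. No decision rule changes. It is still worth correcting, because the remedy is small and these are the patients for whom an Enrolled safety analysis differs from an As-Treated one.

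**What to change.** 1. In Protocol 8.6, state that MAE data are collected through at least day 30 after the index procedure for every Enrolled patient, and that follow-up continues past day 30 if implant-related AEs are unresolved, whichever is later. With complete day-30 follow-up, the Kaplan-Meier error from early exit is zero by construction.
2. Reconcile 8.6 with the synopsis (all enrolled), section 6.3 (all implanted), section 11.9 and Table 14 note B. Keep note B's 30-day safety follow-up for patients without an incision. Redirecting that note to patients with an incision would remove it.
3. Reconcile the population in Protocol 12.4 (implanted) with Protocol 12.2 and SAP 8.1 (Enrolled).
4. In the SAP, say how the day-37 denominator rule treats an event-free patient who exits at day 30; as written, it drops that patient.
5. If patients have already exited early, report their exit days and a sensitivity analysis of the 30-day MAE rate.

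The cost is a protocol amendment, which under Protocol 15.8 needs regulator and IRB agreement, and at most one 30-day safety contact for a few patients. Section 8.6 already offers that follow-up as one of its two alternatives.
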